A peripheral nerve monitor may be used to monitor the degree of residual neuromuscular blockade. This is standard anaesthetic equipment with the most common mode to assess residual blockade used being a train of four count. This involves adhesive dots applied over the ulna nerve and a current applied (approximately 70-80mA) in a train of four impulses 0.5 seconds apart with a pulse width of 250 microseconds. It is a safe method of assessing the occupancy of

acetylcholine receptors at the neuromuscular junction by observing the number of twitches displayed in the peripheral muscle (e.g thumb movement).

Number of twitches

- 0- 100% receptors blocked
- 1- 90% receptors blocked
- 2- 75-80% receptors blocked
- 3- 75% receptors blocked
- 4- 0% receptors blocked

For the purposes of our study we plan to continuously monitor the train of four count and ratio using a peripheral nerve stimulator module that is built into the anesthesia machine (GE Datex Ohmeda). The train of four count on both measuring tools will be delivered as a train of four impulses 0.5 seconds apart (2Hz) at 70-80mA with a pulse width of 250 microseconds.

Our current approach does not involve routine measurement of the degree of residual neuromuscular blockade with a peripheral nerve stimulator. This is a safe approach as monitoring is achievable with partial blockade but may not necessarily be most beneficial in patients with existing neurological impairment as complete reversal of neuromuscular blockade is not ensured.(Li, Song et al. 2010)

The issues with this current technique are;

- a) Patients cannot be monitored for neurological changes during their transfer into the prone position
- b) There is likely residual neuromuscular blockade decreasing the amplitude of motor evoked potentials

A cases series of 10 patients in healthy subjects undergoing lumbar spine surgery demonstrated a 74% increase in mean amplitude of the MEPs with reversal of neuromuscular blockade with sugammadex 2mg/kg.(Batistaki, Papadopoulos et al. 2012)

We plan to perform a randomised controlled cross over trial comparing the change in MEP amplitudes with administration of sugammadex or placebo. This will be performed on at risk patients (e.g. cervical myelopathy) undergoing posterior cervical spine surgery where MEPs can be more difficult to attain but of higher utility.(Kombos, Kopetsch et al. 2003)

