7.2 Study Protocol

Patients should undergo peripheral nerve monitoring following the induction via a peripheral nerve stimulator and by a direct train of four monitor by the neurophysiologists. The train of four should be assessed on peripheral nerve stimulator and on the neurophysiology monitoring prior to turning the patient prone. If the patient has two or more twitches on either monitoring they should be given 0.1mg/kg rocuronium prior to positioning prone.

Once the patient is in their final position for surgery the anaesthetic will be changed to a total intravenous anaesthetic (TIVA) with propofol and remifentanil titrated to entropy of 40-60. The volatile anaesthesia has to be washed out with high flows of 10L/min until end tidal desflurane is less than or equal to 0.2.

When the above conditions are met the train of four count (TOFC) will be checked by the anaesthesiologist. When the TOFC is 2 or more the baseline motor evoked potentials (bMEPs) will be performed.

Following the bMEPs the anaesthesiologist will administer the reversal drug (either sugammadex 2mg/kg in 10 ml syringe or matching placebo). This time must be strictly recorded, as it is the time that has elapsed since the induction dose of muscle relaxant. The neurophysiologist will perform and record MEPS at 3,6 and 9 minutes post reversal dose. The following parameters will continuously be monitored during the study period: TOFC, Entropy, BP, HR, CO2,

peak airway pressures, anaesthetic infusion rates, temperature and oxygen saturation. If the testing occurs during surgical exposure it is important to ask the surgeons to make a very brief pause to allow the motor testing to be performed and to check the entropy at the same time.

Following surgery commencement there will be a surgical grading of the relaxation of the surgical field once exposure attained and collection of surgeon stated observation of patient movement.

The operative time of posterior cervical spine procedure is usually around 3 hours and should allow for complete washout of rocuronium. A minimum washout period of 100 min after the last bolus dose of rocuronium (equivalent to 5 half-lives) is required and the completeness of washout will be confirmed with no residual tetanus fade, no fade on train of four (or fading in double burst stimulation) on a peripheral nerve stimulator.

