The crossover arm of the trial will occur during surgical closure at the end of the operation when the surgeons have finalised their use of the monitoring and the patients are still receiving total intravenous anaesthesia (propofol and remifentanil). If needed, each patient will be given 0.1mg /kg rocuronium to facilitate surgical closure. When the train of four count is of 2 or more the patients will be administered the cross-over drug (placebo if received sugammadex initially and vice versa) and the motor evoked potentials and same anaesthetic variables as above will be recorded for 3,6 and 9 minutes post cross-over dose.

8. Assessment

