10.2 Sample size

A previous observational study reported sugammadex increased the amplitude of MEP by 74% (Batistaki, Papadopoulos et al. 2012). The normal upper limb MEP amplitude (first dorsal interosseus) is 2000 +/- 1600 microV from a previous published cross-over study in MEP (Chong, Manninen et al. 2014). Based on the assumption that the within-patient standard deviation of the MEP amplitude is 1600 microV and a power of 80%, a total of 30 patients is required in this two-intervention crossover study for detecting a treatment difference of 1200 microV (60% increment) at a two-sided 0.05 significance level. The sample size will be increased to 40 patients (20 patients per group) to cater for a potential 15-25% drop-out rate during the study.

11. Analysis

Statistical analysis will be performed using SPSS statistical software (version 14). The data distributions will be tested for normality with the Kolmogorov-Smirnov test. Descriptive statistics will be summarised as mean (\pm SD), median [Interquartile range (IQR)] or number (%) as indicated. The Mann-Whitney U test will be performed to compare the amplitude values of the two groups. TOF count, grades of surgical relaxation will be compared using the Chi-square test or Fisher's exact test according to the expected counts. In all cases, a P-value of 0.05 will be considered statistically significant.

12. Ethical aspects

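### Residual block is compared only as train-of-four count, which stops at 4 and cannot register fade, although the plan already monitors the ratio

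*Combined protocol and SAP*

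**What the plan says.** Section 2 (Background) commits to both measures: "we plan to continuously monitor the train of four count and ratio using a peripheral nerve stimulator module". After that the ratio is not mentioned again. The list of variables followed around each dose in section 7.2 begins "The following parameters will continuously be monitored during the study period: TOFC, Entropy, BP, HR, CO2" and contains the count but no ratio. The crossover part of 7.2 refers back to the same list. Section 8.2 names neither count nor ratio as an outcome. Section 11 provides for one comparison of block: "TOF count, grades of surgical relaxation will be compared using the Chi-square test or Fisher's exact test according to the expected counts".

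Dosing is tied to the count. For the first period, "When the TOFC is 2 or more the baseline motor evoked potentials (bMEPs) will be performed", and the study drug follows. For the second, "When the train of four count is of 2 or more the patients will be administered the cross-over drug". Section 6.1 gives a count of 2, without the words for more, for the first intervention.

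The plan describes full recovery in two ways. The table in section 2 has "3- 75% receptors blocked" and then "4- 0% receptors blocked". For the washout, section 7.2 (and 6.1 similarly) asks for more than four twitches: "the completeness of washout will be confirmed with no residual tetanus fade, no fade on train of four".

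**The concern.** The rationale of the trial is that residual block depresses MEPs and that reversing it raises their amplitude. A reader of the results will want to know whether block really differed between sugammadex and placebo when the MEPs were recorded. The only direct measure of block that section 11 compares is a count that stops at 4.

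By the plan's own washout rule, four twitches do not prove recovery, because fade must be absent as well. The count cannot register fade, and the ratio is there to capture it. If many placebo patients recover to four fading twitches, the count would report similar block under both treatments while block still differed. An MEP difference could then look unconnected with reversal. A null MEP result would be harder to interpret, because the analysed measure of block could not show whether the treatments had produced different degrees of block.

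**Working it through.** **1. The plan's own figure.** No power or sample size is stated for the TOF comparison. The only stated size is for the MEP outcome (section 10.2): within-patient SD 1600 microV, difference 1200 microV, two-sided 0.05, power 80%, 30 patients.

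- Normal approximation: N = 2 × [1600 × (1.960 + 0.842) / 1200]² = 27.9, so 28.
- Noncentral t with N − 2 degrees of freedom: 80.06% power at N = 30.
- Dropout at 25%: 30 / 0.75 = 40.

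The stated size reproduces. It does not involve the TOF count, so nothing below alters it.

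**2. The ceiling, from the text alone.**

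- Entry at 2 or more (7.2) means a baseline count of 2, 3 or 4. A patient who enters at 4 cannot rise.
- The section 2 table puts three twitches at 75% of receptors blocked and four at 0%. Any block between those values has no category except 4.
- Sections 6.1 and 7.2 require absence of fade to confirm washout. That check would be redundant if four twitches meant no block. The washout rule and the table therefore disagree on what a count of 4 means.

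**3. What the ceiling costs if the comparison is made after dosing.** Assumptions that are not in the documents: every sugammadex patient is at count 4, and a share p of placebo patients is also at 4. The count is reduced to 4 versus below 4 and tested by Fisher's exact test, two-sided 0.05. With n per arm and X ~ Binomial(n, p) placebo patients at 4, power = P(X ≤ c), where c is the largest placebo number at 4 that still gives P ≤ 0.05.

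- n = 20: c = 15 (20/20 v 15/20 gives P = 0.047; 20/20 v 16/20 gives P = 0.106).
- n = 40: c = 34 (40/40 v 34/40 gives P = 0.026; 40/40 v 35/40 gives P = 0.055).

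| Share of placebo patients at 4 | 20 v 20 (one period, all enrolled) | 40 v 40 (both periods pooled, pairing ignored) |
|---|---|---|
| 50% | 0.994 | 1.000 |
| 70% | 0.762 | 0.991 |
| 80% | 0.370 | 0.839 |
| 90% | 0.043 | 0.206 |
| 100% | 0 | 0 |

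With the 30 evaluable patients of section 10.2, power at 70%, 80% and 90% is 0.485, 0.164 and 0.013 for one period (15 v 15). It is 0.923, 0.572 and 0.073 for both periods pooled (30 v 30).

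The two columns are both shown because section 11 does not say how the two periods enter the test. Pooling delays the loss but does not remove it. Once all placebo patients are at 4, no sample size helps.

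**The case against.** The strongest reply is that section 11 gives this comparison neither a time point nor a role. Because dosing is triggered by count, it could be a comparison of block depth at dosing, and the argument about placebo patients drifting up to four twitches would then not apply. That stands, and the loss of sensitivity is stated here only for a comparison made after dosing.

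Several stronger readings are tempting, and the documents do not support them.

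- *That the TOF count is the trial's only check on reversal.* Section 8.2 also collects the surgeon's grade of field relaxation, observed movement and need for further relaxant. Sections 7.1 and 7.2 add a direct train-of-four monitor run by the neurophysiologists. The section 8.2 measures are indirect, but they bear on block.
- *That the count will fail.* No document says how many placebo patients reach four twitches by 3, 6 or 9 minutes. At a share of 50% power is 0.994 even at 20 v 20, and at 30% it is practically 1.
- *That the ratio would separate the treatments wherever the count does not.* The documents give no ratio values or SD, so no power can be computed for it. It can register differences that the count cannot, and no more than that is claimed.
- *That the ratio will not be captured at all.* Section 2 plans to monitor it, and the data collection form mentioned in section 9.1 is not in the available text. What can be said is that 7.2, 8.2 and 11 do not name it.

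The use of an independent-groups test on crossover data is a separate weakness, which also affects the Mann-Whitney test for amplitude. It matters here because any replacement comparison should be paired.

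**Conclusion.** The point holds in a limited form. By the plan's own standard for recovery, the block measure chosen for analysis has a ceiling, and a finer measure that the plan already monitors is left out of the analysis. If the comparison is made after dosing and all sugammadex patients are at 4, it weakens as the placebo share at 4 rises above about 70% in one period (power 76%, then 37% at 80%). With both periods pooled it weakens above about 80% (power 84%, then 21% at 90%). These shares are assumptions, and at 50% or below the count is adequate.

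The consequence is for interpreting whether block differed between treatments. The TOF count is not a listed outcome, so this does not bias the MEP estimate or alter the planned 30 evaluable and 40 enrolled patients. It is a worthwhile change to a supporting analysis because it costs so little.

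**What to change.** - **Section 7.2:** record the TOF ratio together with the count at baseline and at 3, 6 and 9 minutes in each period. Section 6.1 also lists 12 and 15 minutes; those schedules should be aligned, and the ratio recorded at whichever MEP times are kept.
- **Section 11:** replace the Chi-square or Fisher comparison of TOF count with a within-patient comparison of the TOF ratio between treatments at those times. Use a paired rank-based method in which an absent fourth twitch ranks lowest, and state the time points. Keep the count as descriptive.
- **Section 2 against 6.1 and 7.2:** reconcile the table line for four twitches with the no-fade rule. Reconcile also the count at first dosing, which is 2 in section 6.1 and 2 or more in 7.2.

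The cost is one more recorded variable and a little more analysis. No new equipment is needed, since section 2 already plans to monitor the ratio with the built-in module.

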The crossover arm of the trial is to enable patients to function as their own control group. During surgical closure patient will remain on a total intravenous anaesthesia (propofol and remifentanil). When the patient returns to a train of four count of 2 or more on peripheral nerve monitor repeat motor evoked potentials will then be recorded and

patients will receive the alternate drug to the one received in the initial arm of the trial.

The purpose of this study is to determine the increase in amplitude of the motor evoked potentials when residual neuromuscular blockade is reversed with sugammadex or placebo.

4. Hypothesis

We hypothesize that reversal of neuromuscular blockade by sugammadex will increase the amplitude of motor evoked potentials compared with placebo.

5. Significance of the study

Facilitating increased amplitudes of MEPS via reversal of residual neuromuscular blockade will enable increased accuracy of monitoring.

Providing the option of reversal of neuromuscular blockade will allow MEPs to be monitored during patient positioning to prevent placing them in a neurologically compromising position.

6. Methods

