6.1 Research Design

This is a prospective, single centre, triple blinded randomised controlled cross-over trial. Patients who are scheduled for an elective posterior cervical spine procedure in prone position and require motor evoked potential monitoring (MEPs) will be included. Patients will be randomised to assign to one of the following treatment sequences: sugammadex followed by placebo, or vice versa. The primary outcome is the change of MEP amplitude of the first dorsal interossei from baseline 3 minutes after administration of the allocated intervention. The patients, anesthesiologists and neurophysiologists (outcome assessor) will be blinded for the allocated intervention group.

The first study intervention will be performed after the patients are positioned in prone with a train of four count of 2 and satisfactory baseline motor evoked potentials have been recorded. This will likely occur during or just prior to surgical exposure.

The second study intervention will be performed during surgical closure. This will be once the surgeons have completed their use of motor evoked potentials and the patient remains on total intravenous anaesthesia (propofol and remifentanil). A minimum washout period of 100 min after the last bolus dose of rocuronium (equivalent to 5 half lives) is required and the completeness of washout will be confirmed with no residual tetanus fade, fade on train of four (or fading in double burst stimulation) on a peripheral nerve stimulator. The operative time

of posterior cervical spine procedure is usually around 3 hours and should allow complete washout of rocuronium. After the preconditions are achieved on peripheral nerve stimulator or the direct train of four monitor, the second intervention (either sugammadex or placebo) will be administered.

On each occasion the increase in amplitude of the motor evoked potential of both upper and lower limbs will be assessed at 3,6,9,12 and 15 minutes post intervention.

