6.4 Randomisation Method

Enrolled patients will be randomised according to a computer based, permuted block randomisation method, with a 1:1 allocation ratio and a variable block size of 4-6.

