8.2 Outcome Measurements

Primary Outcome Measure

The primary outcome measure is the increase in amplitude of the motor evoked potential measurements of the first dorsal interosseous muscle at 3 minutes following reversal of residual muscle relaxation with either sugammadex or placebo.

Secondary Outcome Measures

- Changes in the amplitude of the MEPs from the baseline in the first dorsal interosseous muscle at 6 and 9 minutes

- Side effects of reversal (hemodynamic changes, respiratory changes, surgeon observed patient movement, requirement for additional muscle relaxation and the anesthetic agents)
- Grading of relaxation of the surgical field by the surgeons using a four-point Likert scale (poor, acceptable, good and optimal) .

9. Data Collection and Management

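### Section 11 plans descriptive summaries and P-values, but no within-patient sugammadex-versus-placebo effect with a confidence interval

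*Combined protocol and SAP*

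**What the plan says.** The purpose statement just before Section 4 (Hypothesis) is about size: "The purpose of this study is to determine the increase in amplitude of the motor evoked potentials". Section 8.2 makes that quantity primary: "The primary outcome measure is the increase in amplitude of the motor evoked potential measurements of the first dorsal interosseous muscle at 3 minutes".

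The design is a two-sequence crossover. Section 6.1 states: "Patients will be randomised to assign to one of the following treatment sequences: sugammadex followed by placebo, or vice versa". Section 10.2 sizes the trial on a treatment difference of 1200 microV, given as 60% of a 2000 microV reference. It assumes that "the within-patient standard deviation of the MEP amplitude is 1600 microV and a power of 80" per cent, "at a two-sided 0.05 significance level". This gives 30 patients, raised to 40 for drop-out of 15 to 25%.

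Section 11 (Analysis) plans:

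- a Kolmogorov-Smirnov check of normality;
- summaries as mean (SD), median [IQR] or number (%);
- a Mann-Whitney U test of amplitude between two groups;
- chi-square or Fisher tests for TOF count and surgical relaxation;
- one decision rule: "In all cases, a P-value of 0.05 will be considered statistically significant".

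Neither Section 11 nor any other section names a treatment difference or ratio, a confidence interval, or a paired or crossover model that would produce them.

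**The concern.** The quantity that the trial is built to measure, and on which it is sized, is never estimated with a statement of precision. The only inferential output for the primary outcome is the P-value of a test for two independent groups.

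Two things are lost. First, a reader could subtract one group summary from the other but could not attach an interval. In a crossover the uncertainty depends on the SD of the within-patient difference, and the two separate SDs or IQRs do not supply it. Second, a non-significant P-value does not show whether the data rule out 1200 microV or are merely too imprecise to detect it. A significant one does not show whether the effect is near nil or above target.

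This is distinct from the choice of an unpaired test. Moving to a paired rank test would restore the pairing and still leave a bare P-value unless the estimate and interval are requested.

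**Working it through.** **Inputs (Section 10.2).** Within-patient SD 1600 microV; target 1200 microV; reference mean 2000 microV; two-sided 0.05; 80% power; 30 evaluable patients, 40 enrolled.

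**Step 1: reproduce the sample size.**
- Normal approximation for the crossover total: 2 × (1600 × (1.960 + 0.842) / 1200)² = 27.9, so 28.
- Noncentral t, with SD of the within-patient difference √2 × 1600 = 2263 and N − 2 degrees of freedom: N = 29 gives 78.6% power and N = 30 gives 80.1%. The stated 30 is reproduced.
- Drop-out: 30 / (1 − 0.25) = 40, also reproduced.

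Taking 1600 as the SD of the difference itself would give 14 patients, so the √2 reading is the one consistent with the plan.

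**Step 2: precision of the missing interval.** Half-width = t(0.975, N − 2) × √2 × 1600 / √N.
- N = 30: SE = 2263 / √30 = 413; 2.048 × 413 = 846 microV (42% of 2000).
- N = 40: SE = 2263 / √40 = 358; 2.024 × 358 = 724 microV (36% of 2000).

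**Step 3: which non-significant results are ambiguous?** An estimate is non-significant below the half-width, and its interval still reaches 1200 if the estimate is at least 1200 minus the half-width.
- N = 30: 1200 − 846 = 354, so the ambiguous band is about 354 to 846 microV.
- N = 40: 1200 − 724 = 476, so about 476 to 724 microV.

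Two examples at N = 30: an estimate of 700 has interval −146 to 1546 (non-significant, includes 1200); an estimate of 850 has interval 4 to 1696 (significant, from almost nil to 1.4 times the target).

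**Step 4: how often this matters** (400,000 simulated trials per setting, normal data, SD estimated in each).

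| True effect | N | Non-significant | Of those, CI includes 1200 |
|---|---|---|---|
| 1200 | 30 | 20% | 88% |
| 1200 | 40 | 9% | 75% |
| 0 | 30 | 95% | 18% |
| 0 | 40 | 95% | 8% |

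The interval would therefore usually separate a null effect from a missed planned effect.

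**Step 5: can the interval be rebuilt from the planned summaries?** Only by treating the data as two independent groups with SD 1600. Half-width is then t × 1600 × √(2/n): 1024 microV for 20 v 20 and 1197 for 15 v 15. Neither is the crossover interval.

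**Range for the SD.** The 1600 is stated for amplitude, while the outcome is a change from baseline.
- If the SD of the within-patient difference were only 1600, the half-width at N = 30 would be 2.048 × 1600 / √30 = 598, and the band would vanish (1200 − 598 = 602, above 598).
- If 1600 applied independently to each of the four readings (two baselines, two post-dose), the SD would be √4 × 1600 = 3200, the half-width 2.048 × 3200 / √30 = 1197, and the band about 3 to 1197.

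**The case against.** The strongest reply is that Section 11 is not confined to P-values. It plans means with SDs or medians with IQRs, and since the outcome is itself a change, these describe the size of the increase under each treatment. If means are reported and every patient completes both periods, the difference of the two means equals the mean within-patient difference. This stands, so a reader who infers that the plan cannot say anything about size goes too far. What is missing is a named contrast and its precision; with medians, even the point figure is not the within-patient one.

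The opening aim, the hypothesis and Section 10.1 are also framed as comparisons or tests of difference, so this is not purely an estimation trial. That is fair, but the purpose statement and the sample size both rest on a magnitude.

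A reader might further infer that P above 0.05 will be taken as no effect. The documents do not say so; Section 11 defines only what counts as significant. Nor is every non-significant result ambiguous: below about 354 microV at N = 30, the interval excludes 1200.

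An interval would not narrow the uncertainty, which comes from N and the SD. It would show it, and that is the purpose.

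Finally, a Mann-Whitney test on period differences between the two sequences would be a proper crossover analysis, but Section 11 applies the test to amplitude values.

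**Conclusion.** The point holds in limited form: the plan has descriptive summaries and P-values, but no within-patient treatment effect with a confidence interval, although its purpose and sample size rest on one. On the plan's SD the unreported half-width is about 846 microV at 30 patients and 724 at 40, against a target of 1200. At 30 patients, estimates of about 354 to 846 microV would be non-significant and still compatible with the target.

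These figures assume roughly normal within-patient differences and carry the 1600 microV over from amplitude to change from baseline. The width of the band depends on that SD; the absence of the estimate and interval does not. The sample size reproduces and is not at fault. The documents do not support saying that the trial cannot meet its purpose, or that a non-significant result could never be distinguished from the planned effect.

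**What to change.** In Section 11, replace the Mann-Whitney comparison as the primary result. Specify instead the within-patient sugammadex-minus-placebo difference in change from baseline of first dorsal interosseous MEP amplitude at 3 minutes, in microV (the scale of the sample size). Estimate it from a crossover model with sequence and period terms, and report it with its 95% CI and the P-value alongside.

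If normality fails, by a rule fixed in advance, use the rank-based crossover counterpart: the Hodges-Lehmann shift in period differences between sequences, halved to the treatment-effect scale, with its 95% CI.

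State that a non-significant result will be read against 1200 microV using the interval. Report the 6- and 9-minute outcomes of Section 8.2 in the same way.

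The cost is a few sentences of plan text and slightly more analysis work. Sample size, procedures and data collection do not change.
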